Lay Summary – Complete dentures represent the traditional dental treatment for patients without teeth. However, retention and stability of this type of denture are often lacking, so dental implants are indicated in order to improve the stability of the denture, along with the satisfaction of the patient. Usually, the dental implants are inserted and then a period of 3-6 months is waited before any denture is connected to them. Recent studies have demonstrated that connecting the lower denture to the implants immediately after the implant placement, leads to an improvement in the result, with a social and psychological benefit for the patient. Therefore, the aim of this research project is to evaluate the application of the immediate connections of the implants for the upper dentures. 15-40 patients wearing an upper denture will receive 4 dental implants and the denture will be immediately connected. To simplify the surgical procedure, the implants will be placed without exposing the bone. This surgical technique is called guided surgery. Secondary objective of this research project will be the evaluation of the precision of the implant positioning, using this specific technique. The patients will be followed up for 12 months, for the implant and denture evaluation, as well as the evaluation of patient satisfaction and impact on quality of life through questionnaires.

Study Population – Total number of patients is from a minimum of 15 subjects to a maximum of 40. This research project is aimed at patients who wear a complete maxillary denture and would like to improve its stability with the use of dental implants. Patients will be recruited within WVU dental clinics. Patients identified as potential candidates will be evaluated by the PI and CO-Is. If the patient meets the requirements, the patient will be contacted by the dentist, and PI and Co-Is will be presenting the protocol. The Principal Investigator, Sub-Investigators, and Study Coordinators working closely together to identify potential study participants. If a particular patient is found to meet the inclusion criteria, the PI and or Study Coordinator are alerted so that they may determine eligibility. If eligibility is met, the patient is usually approached by their treating dentist, who may also be the PI or Co-I, and the study introduced during their routine clinic visit.

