Study Design – This study will be performed at the WVU School of Dentistry. Total number of patients is from a minimum of 15-40 subjects. Each subject will receive 4 implants. Implants will be placed flapless using a guided surgical protocol and will be immediately loaded by means of a NOVALOC TiN retained maxillary overdenture. The patients will be followed up for 12 months, with a total of at least 8 visits (screening, surgery, 1 week, 2 weeks, 4 weeks, 3 months, 6 months, 12 months).

Study Duration – The estimate start of the study is planned to be June 2018. The enrollment of participants will be performed for 2 years, approximately until June 2020. Data collection and analysis will be concluded in June 2021.

Section II: Design

Background & Significance

Since the first application, implant-supported overdentures have been shown to be a reliable and long-term predictable treatment option for completely edentulous patients in terms of both prosthodontic and implant outcomes (Attard, et al., 2004). Besides providing retention and stability, dental implants assist in reducing the impact of tissue borne edentulous prosthesis and are considered the best option when the patient is not able to acquire new muscular patterns and cope with complete dentures (Mericske-Stern, 1994): it has been reported that implant rehabilitations slow the rate of residual ridge resorption (Adell, et al., 1981), increase the masticatory efficiency (Geertaman, et al., 1994) (Mericske-Stern, 1998) and improve the stability and retention of dentures (Jemt, et al., 1996). Moreover, compared to the conventional removable prosthesis, implant overdentures result in an improvement of the general health-related quality of life, with an evident social and psychological impact for the benefit of the patient (Heydecke, et al., 2003). In particular, according to a recent prospective study, patient satisfaction significantly increased for implant-supported maxillary dentures compared with old dentures in all seven OHIP parameters (functional limitation, physical pain, psychological discomfort, physical disability, psychological disability, social disability, handicap), as well as for cleaning ability, general satisfaction, ability to speak, comfort, esthetics, and stability (Zembic, Wismeijer 2014).

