In order to avoid or limit the need of bone augmentation, reduced diameter implants have been introduced. Narrow implants have been used for different applications, such as limited tooth-to-tooth spacing (Reddy, et al., 2008) (Cordaro, et al., 2006), partially edentulous patients (Barter, et al., 2012) (Romeo, et al., 2006), edentulous mandibles (Flanagan, 2011) and recently also edentulous maxillae (Veltri, et al., 2008) (Hallman, 2001). In particular, a recent study (Cannizzaro, et al., 2007) evaluated the use of reduced diameter implants made of Ti-Zr alloy supporting maxillary overdentures retained with locator abutments: after 12 to 16 months of follow-up, no implants were lost, only one implant showed bone resorption greater than 1.5 mm, with an overall success rate of 97.5% and a survival rate of 100%. In that study, Ti-Zr implants were used, in order to compensate the potential drawback of the reduced diameter titanium implants, that is a lower mechanical strength, with the related risk of fracture, especially at the implant-abutment interface.

During the last decades, particular attention has been focused on the computer-guided and –navigated surgery, with the development of different strategies to transfer the digitally planned implant positions to the patient (Van Assche N, 2012). This methodology has been shown to have numerous advantages: high precision in the implant placement, maximization of bone anchorage to the implant, reduction of surgical time and reduction of patient morbidity (Vercruyssen, et al. 2014). For this reason, nowadays computer-guided surgery is a validated and reliable option for implant placement.

Considered the insufficiency of clinical documentation for immediate loading protocols in maxilla, the aim of this study is to assess the clinical and radiographic performance of Roxolid™ 3.75 mm implants 12 months post-loading supporting a maxillary overdenture, using a flapless guided surgery and an immediate loading protocol.

Objectives

Purpose – The purpose of the study is to evaluate the radiographic, clinical and patient-related outcomes of implant-

WVU+kc Protocol #: 1801929813

PI: [name]

Approved:15-Dec-2021Expires:14-Dec-2022Number:1801929813

retained immediately-loaded maxillary complete dentures..

Null Hypothesis

No difference in the radiographic and clinical parameters between baseline, 6 and 12 months post-operative intervals.

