Primary Objective – The primary objective of this study is to evaluate radiographically at 6 and 12 months post-loading the performance of the Roxolid™ BLX 3.75 mm implants placed using a flapless guided surgery and immediately loaded with a maxillary overdenture. The outcome will be evaluated using peri-implant, radiographic bone level changes from baseline to 6 and 12 months post implant placement.

Secondary Objective(s) – The secondary objectives include evaluation of:

- Condition of the peri-implant mucosa (pocket depth and bleeding on probing).
- Implant stability quotient (ISQ) at baseline and 12 months
- Implant survival at 6 months and 1 year
- The nature and the frequency of surgical and prosthetic complications
- Patient-centred outcomes (OHIP 14)
- Accuracy of the implant placement (additional CBCT is required)

Study Design & Methodology

General overview

This study will be performed at the WVU School of Dentistry. Total number of patients is from a minimum of 15/20 subjects. Each subject will receive 4 implants. Implants will be placed flapless using a guided surgical protocol and will be immediately loaded by means of a locator retained maxillary overdenture. The study is an Investigator Initiated Project: Straumann accepted to partly sponsor the study, providing some financial support and materials (implants and abutments). Also, study participants will receive \$100 as reimbursement for travel expenses for each of the 3 months, 6 months and 12 months recall visits, (visit 6,7, and 8 as per visit schema) for a total of \$300 .

Pre-treatment procedures

An initial evaluation will be conducted to determine whether a patient meets the study inclusion criteria. This evaluation will include medical history, clinical examination and radiographic examination (OPT). A pre-operative prosthetic evaluation of the existing prostheses will be made to establish their quality and the need for a new set of complete dentures before the implant placement. The maxillary denture will be used as radiographic guide for the pre-treatment CBCT assessment. The tridimensional image obtained with the CBCT will be used for the surgical planning of the implant positioning by means of a dedicated implant planning software (coDiagnostix, Dental Wings Gbmh, Chemniz Germany)) and a stereo-lithographic surgical guide will obtained.

Surgical procedures

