Prosthetic complications

The number and nature of prosthetic complications will be recorded as well as the number and nature of any unplanned visit for each group.

Patient-centered outcomes

Patient centered outcomes will be recorded through the Oral Health Impact Profile (OHIP-14), which is a 14-items questionnaire designed to measure self-reported functional limitation, discomfort and disability attributed to oral conditions (Slade 1997). The OHIP-14 has been shown to be reliable (Slade 1997); sensitive to changes (Locker, Jokovic e Clarke 2004) and it has adequate cross-cultural consistency (Allison, et al. 1999).

Accuracy of the guided system

The Software will compare the actual position of the implants with the pre-surgical planned placement. Difference in angulation and depth will be recorded. A second CBCT will be performed immediately after the surgical placement of the implants.

Target Population & Recruitment Methods

The study population consists of 15-40 patients (15 minimum, 40 maximum), male or female ≥ 21 years of age, requiring 4 implants supported maxillary overdenture. The enrollment of patients will be open to a diverse racial and ethnical backgrounds in order to ensure equitable selection.

Inclusion Criteria – Inclusion criteria include:

- Males and females must be at least ≥ 21 years of age
- Fully edentulous maxilla
- The implant site has to be healed for at least 4 months after extraction
- Wearing complete dentures deemed adequate
- Orthopantomogram available (OPT)
- Adequate amount of bone at least at the 2nd premolar position to house a 3.75 x 10 mm implant
- No bone grafting required
- Implant IT ≥ 20 N/cm

Exclusion Criteria – These are both systemic and local exclusion criteria:

Systemic exclusion criteria

- Conditions requiring chronic routine prophylactic use of antibiotics
- Conditions requiring prolonged use of steroids
- History of leukocyte dysfunction and deficiencies
- Bleeding disorders
- History of neoplastic disease requiring use of radiation or chemotherapy
- Metabolic bone disorders
- Uncontrolled endocrine disorder
- Use of any investigational drug or device within the 30-day period prior to implant surgery
- Smoking more than 10 cigarettes a day
- Alcoholism or drug abuse
- Patient infected with HIV

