Risk – The risks for the participants are represented by the possible complications from the surgical procedure, which may include: implant failure, pain; postoperative discomfort; swelling; restricted mouth opening that may last for several days; bleeding; infection requiring additional treatment; stretching of the corners of the mouth resulting in cracking and/or bruising; change in the occlusion (bite); jaw joint pain; fracture of the jaw; injury to nerve branches; numbness or tingling of the lip, gums, cheek that may last for several months.

Benefit – The advantages of implant rehabilitations for the patients include: improved stability and retention of denture; increased masticatory efficiency; slower rate of bone ridge resorption. In particular, according to a recent prospective study, patient satisfaction significantly increased for implant-supported maxillary dentures compared with old dentures in all seven OHIP parameters (functional limitation, physical pain, psychological discomfort, physical disability, psychological disability, social disability, handicap), as well as for cleaning ability, general satisfaction, ability to speak, comfort, esthetics, and stability (Zembic, Wismeijer 2014). The single patient may not receive any direct benefit from this study. The knowledge gained from this study may eventually benefit others.

Statistical Analysis Plan

Primary outcome variables will test for normal distribution and two-way Paired t test or Student t-test will be used to compare the means. Descriptive statistics will be used to describe patient population. Non-parametric inferential

statics will be used for ordinal/non-parametric data set. The chosen sample size will provide enough power to deliver significant results.

Data Safety Monitoring – Any information that is obtained as a result of this research will be kept as confidential as legally possible. The research records and test results may be subpoenaed by court order or may be inspected by the study sponsor or federal regulatory authorities without your additional consent. In any publications that result from this research, neither name nor any information from which the patients might be identified will be published without their consent.

Safety Monitoring & Unanticipated Event Reporting

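### The power assurance has no stated sample size, alpha, effect or SD behind it, and a test of zero change is not the primary result the study needs: report patient-level mean bone level change with a 95% CI

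*Combined protocol and SAP*

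**What the plan says.** **Sample size.** The Statistical Analysis Plan says: "The chosen sample size will provide enough power to deliver significant results". The size is given as a range. Study Population has "Total number of patients is from a minimum of 15 subjects to a maximum of 40", Study Design has "Total number of patients is from a minimum of 15-40 subjects", and Target Population & Recruitment Methods repeats 15 to 40. The General overview under Study Design & Methodology has "Total number of patients is from a minimum of 15/20 subjects", with no maximum. No significance level, numeric power, target change, SD or calculation appears anywhere.

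**Primary outcome and analysis.** The Primary Objective is evaluated by "radiographic bone level changes from baseline to 6 and 12 months post implant placement". The Null Hypothesis section reads: "No difference in the radiographic and clinical parameters between baseline, 6 and 12 months post-operative intervals". For primary outcome variables the Statistical Analysis Plan foresees a normality check, after which a "two-way Paired t test or Student t-test will be used to compare the means"; non-parametric tests are kept for data that do not suit this. Descriptive statistics are planned only for the patient population, and no confidence interval is mentioned.

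**Unit of measurement.** Under Radiographic bone level, the mesial and distal readings are averaged to one value per implant. Each patient receives four implants. The unit of analysis is not stated.

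**The concern.** Three linked things are at stake.

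- **The assurance cannot be checked.** Power depends on the number of patients, the significance level and the change to be detected relative to its SD. The first is a range and the others are absent.
- **The test does not match the aim.** The study has one arm and aims to assess radiographic performance. Rejecting zero change shows only that bone level moved. Failing to reject it with few patients does not show stability. What informs the aim is the size of the change and its precision, and the plan does not commit to reporting either.
- **The unit is open.** Four implants in one mouth share a patient, a denture and an operator, so their bone level changes are likely to be correlated. A t-test on per-implant values would count them as independent, and its standard error would be too small.

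**Working it through.** The plan offers no figure to reproduce. The calculations below show what its range implies.

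**Inputs from the documents:** 15 to 40 patients, with 20 from the 15/20 wording; four implants per patient; a paired comparison with baseline.

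**Assumptions:** two-sided alpha 0.05; patient as the unit; roughly normal changes; n = patients evaluable at the visit. SD means the SD of the patient-mean RBL change, which the documents do not give.

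**1. Power.** For a true change of d SD, the test statistic is noncentral t with n − 1 degrees of freedom and noncentrality d√n. Power is the probability that it exceeds t(0.975, n − 1) in absolute value.

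| n evaluable | Change detectable with 80% power | Power, d = 0.3 | Power, d = 0.5 | Power, d = 0.8 |
|---|---|---|---|---|
| 15 | 0.78 SD | 19% | 44% | 82% |
| 20 | 0.66 SD | 25% | 56% | 92% |
| 40 | 0.45 SD | 46% | 87% | >99% |

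Whether power is sufficient depends on which n and which d are meant.

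**2. Precision.** The 95% CI half-width is t(0.975, n − 1) × SD / √n.

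- n = 15: 2.145/√15 = 0.554 SD
- n = 20: 2.093/√20 = 0.468 SD
- n = 40: 2.023/√40 = 0.320 SD

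The ratio between the ends of the range is 0.554/0.320 = 1.73. In mm, for assumed SDs of 0.3, 0.5 and 0.8 mm:

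| n evaluable | SD 0.3 mm | SD 0.5 mm | SD 0.8 mm |
|---|---|---|---|
| 15 | 0.17 | 0.28 | 0.44 |
| 20 | 0.14 | 0.23 | 0.37 |
| 40 | 0.10 | 0.16 | 0.26 |

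These are planning values. They are exact only in units of the SD that is eventually observed. Because that SD varies by chance, at n = 15 the realised half-width would fall between about 0.35 and 0.76 true SD in 95% of studies: 0.554 × √(χ²/14), with χ² at its 2.5% and 97.5% points on 14 degrees of freedom.

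**3. What a non-significant result leaves open.** A non-significant observed loss m satisfies 0 ≤ m < half-width, so its upper 95% limit lies between one and two half-widths: 0.55 to 1.11 SD of bone loss at n = 15, and 0.32 to 0.64 SD at n = 40 (in observed SDs).

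**4. If the t-test were run on implants.** With four implants per patient and intra-patient correlation ICC, the variance of the mean is inflated by 1 + 3 × ICC relative to independence. For 15 patients and 60 implants:

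- ICC 0.2 (assumed): inflation 1.6, so the standard error is too small by √1.6 = 1.26. The critical value t(0.975, 59) = 2.00 acts as 2.00/1.26 ≈ 1.58, and the two-sided type I error is about 11%.
- ICC 0.5 (assumed): inflation 2.5, √2.5 = 1.58, 2.00/1.58 ≈ 1.27, and the type I error is about 21%.

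The type I error uses a normal approximation, which runs slightly low with so few patients.

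**The case against.** The strongest reply is that this is a small single-arm study, that a paired t-test and its CI rest on the same estimate and standard error, and that the study may well have adequate power for a large change. All of that is fair. With 15 evaluable patients, power for 0.8 SD is 82%. But the plan does not say that the estimate or interval will be reported, or on what unit, and the assurance is given without qualification.

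Four stronger readings are tempting, and the documents do not support them:

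- **The study is underpowered.** Without an SD or target change this cannot be shown. At 40 evaluable patients, power for 0.5 SD is 87%.
- **Low insertion torque will cut the numbers below the stated range.** Surgical procedures and the local exclusion criteria do remove patients below 20 N/cm. But the inclusion criteria also require at least 20 N/cm, so the 15 to 40 may already mean patients who met it. The documents give no loss rate.
- **The plan analyses implants as independent.** It does not say so; it leaves the unit open.
- **The plan will read non-significance as stability.** It does not say that either.

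Two further objections stand in part. Precision in SD units follows from n alone, so it informs only alongside an assumed SD in mm. And the approval stamp (December 2021) falls after the planned end of data collection and analysis (June 2021). Enrolment status is not stated, but if it has closed, the precision statement should use the achieved number, and the analysis change becomes the main part of the fix.

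**Conclusion.** The point holds in this form. The power statement is unsupported, not false. Across the permitted range, power for a 0.5 SD change runs from 44% to 87%, and the expected half-width from about 0.55 to 0.32 SD. A test of zero change, parametric or not, does not by itself answer the aim of assessing radiographic performance. The success criteria under Implant Failure/Success do not fill the gap: they apply to each implant, stand apart from the RBL test and contain no mm value. The open unit of analysis matters because the per-implant reading would give a type I error of about 11% to 21% at the correlations assumed here, with 15 patients.

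The power and precision figures rest on a two-sided 5% level, the patient as unit and near-normal changes; a non-parametric analysis would give somewhat different values. The absence of a stated size, alpha, effect and SD, and of a unit of analysis, rests on the text alone. This should be fixed before analysis.

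**What to change.** 1. Make the primary result the mean RBL change from baseline at 6 and at 12 months, each with a 95% CI. Average the four implants within patient, or fit a model with a patient random effect. Keep the paired test, at patient level, as supporting.
2. Replace the power sentence with expected precision. For example: the 95% CI for the patient-level mean RBL change is expected to have a half-width of about 0.55, 0.47 or 0.32 SD with 15, 20 or 40 evaluable patients. Give the mm equivalents for a range of SDs, labelled as assumptions.
3. Say whether 15 to 40 counts enrolled or evaluable patients, and align the General overview with that range.

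**Cost.** Wording changes and a minor analysis change; no added patients, visits or radiographs, since the range is kept. The downsides are that an unqualified assurance gives way to less favourable precision figures, and that the intervals may be wider than in an implant-level analysis. The fix does not set a single target number; it lets the reader judge both ends of the range.
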